2.2 Secondary Objective(s)

- To assess the safety of imetelstat in subjects with MDS
- To assess the time to RBC TI and duration of RBC TI
- To assess the rate of hematologic improvement
- To assess the rates of complete remission (CR), partial remission (PR), or marrow complete remission (mCR)
- To assess overall survival (OS)
- To assess progression free survival (PFS)
- To assess time to progression to acute myeloid leukemia (AML)
- To assess the rate and amount of supportive care, including transfusions and myeloid growth factors (Part 2 only)
- To evaluate the pharmacokinetics and immunogenicity of imetelstat in subjects with MDS
- To assess the effect of treatment on medical resource utilization (Part 2 only)
- To assess the effect of imetelstat on corrected QT (QTc) interval in subjects in the Ventricular Repolarization substudy (to be reported separately from Part 2)

2.3 Exploratory Objective(s)

- To assess the effect of imetelstat treatment on patient-reported outcomes (PROs)
- To evaluate pharmacodynamic biomarkers such as telomerase activity (TA), telomere length (TL) and human telomerase reverse transcriptase (hTERT) and to explore the association between baseline results and clinical response
- To evaluate change of cytogenetic abnormalities and explore the association between baseline cytogenetic status and clinical response
- To evaluate baseline mutational status and mutation changes during treatment for exploring the association with clinical response
- To explore the effects of imetelstat on immune profiles through immunophenotyping (Part 1 only)
- To evaluate the exposure-response relationship between pharmacokinetics and pharmacodynamic biomarkers, efficacy and safety

3 INVESTIGATIONAL PLAN

3.1 Overall Study Design and Plan

This is a Phase 2/3, multicenter study of imetelstat in transfusion-dependent subjects with low or intermediate-1 risk MDS that is relapsed/refractory to ESA treatment. The study will consist of 2 parts, and approximately 270 subjects will be enrolled (57 subjects were enrolled in Part 1(Phase 2), approximately 170 subjects will be enrolled in the main study in Part 2 (Phase 3), and approximately 45 subjects will also be enrolled in a separate Ventricular Repolarization substudy).

Part 1 was an open-label, single-arm Phase 2 design to assess the efficacy and safety of imetelstat. 57 subjects including the expansion cohort were enrolled and followed up for safety, hematologic improvement and reduction in transfusion requirement. The sponsor has reviewed and assessed all available data in Part 1, including blood counts, transfusion requirement, tolerability, pharmacokinetics, and pharmacodynamic biomarker data prior to initiating Part 2.

The futility criteria before Protocol Amendment 2 were defined as follows: If 4 or fewer subjects among 30 subjects in Part 1 achieve RBC TI lasting at least 8 weeks, the study will be stopped unless there is compelling clinical evidence of efficacy in one or more other endpoints (e.g. transfusion reduction, erythroid improvement). Upon review of the efficacy and safety data observed with the 7.5 mg/kg dose among 32 subjects in Part 1, a subset of 13 subjects was identified with higher hematologic response rates. These were subjects with non-del(5q) MDS and without prior exposure to either hypomethylating agents (HMAs) or lenalidomide. As of Amendment 2, Part 1 was expanded to include only subjects who meet these criteria, with the goal to confirm the safety and efficacy data seen in this subset thus far and to re-confirm the dose. Twenty-five additional subjects with non-del(5q) MDS and without prior exposure to either HMAs or lenalidomide, so called target population, were enrolled for a total of 38 (out of 57 subjects overall enrolled in Part 1).

Parexel International

Geron Corporation
63935937MDS3001

Statistical Analysis Plan

Since data from Part 1 for this target population show clinical benefit of treatment with imetelstat, Part 2 of the study will be initiated in subjects with non-del(5q) MDS and without prior exposure to either HMAs or lenalidomide.

Part 2 is a double blind, randomized Phase 3 design to compare the efficacy of imetelstat with placebo. Approximately 170 subjects will be randomized in a 2:1 ratio to receive either imetelstat or placebo, respectively. Randomization will be stratified by prior RBC transfusion burden (≤ 6 or > 6 units RBC) and by International Prognostic Scoring System (IPSS) risk group (low risk versus intermediate-1 risk). Prior RBC transfusion burden is defined as the maximum number of RBC units transfused over an 8-week period during the 16 weeks prior to Cycle 1 Day 1 (C1D1) for subjects enrolled in Part 1 or the day of randomization for subjects enrolled in Part 2. In addition to the main study of Part 2, a separate Ventricular Repolarization substudy will enroll approximately 45 subjects to be randomized 2:1 to receive either imetelstat or placebo investigating the effects of imetelstat exposure on ventricular repolarization.

The randomization schedule will be prepared by an independent statistician not otherwise involved with this study and will be implemented within an interactive web response system (IWRS). Blinded treatment will be used for Part 2 to minimize the potential influence of treatment assignment knowledge on clinical decision making, and to reduce potential bias during data collection and evaluation of clinical endpoints, thus ensuring the robustness and integrity of the study. It is the intent that all subjects, investigators and study team members, except some required project roles, will remain blinded to treatment group assignment at least until the primary efficacy analysis (12 months after the last subject is randomized in the main study of Part 2) and the database is finalized. Subjects and investigators may be unblinded after primary efficacy analysis depending on the outcome of the primary efficacy analysis, potential DMC recommendations and/or interactions with health authorities. The study data sources with the potential to cause unblinding risks and the required project roles with appropriate restricted access to these data sources, and other measures to prevent the identification of study treatment(s) until all such opportunities for bias have passed, are described in a separate Blinding Maintenance Plan.

The Sponsor will review safety data on an ongoing basis to ensure the safety of the subjects enrolled in the study. All hepatic adverse events (AEs) and liver function test abnormalities will be reviewed at least on a quarterly basis, or more frequently if needed, by an Independent Hepatic Expert Committee throughout the study.

An independent DMC will be established to monitor safety data. The DMC will consist of at least 2 medical experts in the relevant therapeutic area and at least 1 statistician. For Part 1 of the study, the DMC performed ad hoc expedited reviews of any \geq Grade 4 hemorrhagic event occurring on the study or any other safety concerns identified by the sponsor. For Part 2 of the study, the DMC will meet periodically and hold ad hoc meetings if required to review unblinded reports for safety as well as efficacy to evaluate risk versus benefit. After each review, the DMC will make recommendations regarding the conduct of the study. The roles, responsibilities and memberships of the DMC and study team are described in a separate DMC Charter.

An independent review committee (IRC) will be established to adjudicate investigator-assessed disease response (CR, PR, mCR, or cytogenetic response) and response (CR, PR, mCR, or cytogenetic response) for subjects with >5% baseline bone marrow aspirate blasts based on the central pathology reviewer's assessment. The IRC will assess responses based on the modified IWG Response Criteria 2006 for MDS. The IRC responsibilities, authorities, and procedures will be documented in a charter.

3.2 Endpoints

Additional details and definitions are provided in Section 4.

3.2.1 Primary Efficacy Endpoint

The primary efficacy endpoint of this study is the rate of RBC TI lasting at least 8 weeks. The 8-week RBC TI rate is defined as the proportion of subjects without any RBC transfusion during any consecutive 8 weeks (56 days) starting from Study Day 1 until subsequent anti-cancer therapy if any. Study Day 1 is defined as the day of the first dose for subjects enrolled in Part 1 and the day of randomization for subjects enrolled in Part 2. The starting date of 8-week RBC TI duration must be between Study Day 1 and the date of last dose of study drug + 30 days or End of Treatment Visit whichever occurs first, or Study Day 31 if randomized but not treated.

3.2.2 Secondary Endpoints

- Safety of imetelstat in subjects with MDS (eg, incidence, intensity, and type of adverse events, vital signs measurements, clinical laboratory values, ECGs changes, and deaths);
- 24-week RBC TI rate, defined as the proportion of subjects without any RBC transfusion during any consecutive 24 weeks (168 days) starting from Study Day 1;
- Time to the 8-week (24-week) RBC TI, defined as the interval from Study Day 1 to the first day of the first 8-week (24-week) RBC TI period;
- Duration of RBC TI, defined as the first day of the longest RBC TI period to the date of the first RBC transfusion after the TI period starts;
- Rate of hematologic improvement, including hematologic improvement-erythroid (HI-E), per modified International Working Group (IWG) 2006;
- Rates of CR, PR, or mCR per modified IWG 2006;
- OS, defined as the interval from Study Day 1 to death from any cause. Survival time of living subjects will be censored on the last date a subject is known to be alive or lost to follow-up;
- Progression free survival, defined as the time interval from Study Day 1 to the first date of disease progression or death from any cause, whichever occurs first.
- Time to progression to AML, defined as the interval from Study Day 1 to the date of AML diagnosis.
- Amount and relative change in RBC transfusions;

- Rate of myeloid growth factors usage, defined as the proportion of subjects receive any myeloid growth factors starting from Study Day 1; duration of myeloid growth factor administered starting from Study Day 1;
- Pharmacokinetic parameters (eg, C_{max} , AUC_{0-t}), and immunogenicity of imetelstat (eg, antibodies to imetelstat);
- Medical resource utilization data including hospitalization, emergency room visits, and hematology specialist visits (Part 2 only);
- ECG parameters including change in QT interval by Fridericia's correction method ($\Delta QTcF$) in the Ventricular Repolarization substudy (Part 2 only).

3.2.3 Exploratory Endpoints

Exploratory endpoints are not applicable for subjects participating in the Ventricular Repolarization substudy (after Protocol Amendment 7);

- TA and hTERT at baseline and the change from baseline, TL at baseline only;
- Cytogenetic status at baseline and change over time for cytogenetic response;
- Mutation status at baseline and change over time including at the time of suspected response (CR, PR, HI-E [hemoglobin (Hb)]) or pharmacodynamic(s) (PD);
- Immune profiles at baseline and change from baseline (Part 1 only);
- Assessment of Quality of Life in Myelodysplasia Scale (QUALMS), Functional Assessment of Cancer Therapy - Anemia-Related Effects (FACT-An), and EuroQol-EQ-5D-5L (EQ-5D-5L).

4 STATISTICAL METHODS

4.1 Data Quality Assurance

All tables, figures and data listings to be included in the report will be independently checked for consistency, integrity and in accordance with standard PAREXEL procedures.

4.2 General Analysis Definitions

4.2.1 Baseline and Phase

Unless specified otherwise, the baseline value is defined as the last non-missing value collected from the local laboratory on or before the first dose of study drug for Part 1 and Part 2. For subjects who have been randomized but not treated with any study drug, the randomization date will be used as the reference date for baseline value calculation. For the purpose of analysis, the term "study drug" refers to imetelstat for Part 1, and imetelstat/placebo for Part 2.

For efficacy analysis that relates with Hb, i.e. HI-E (Hb), pretreatment Hb will be used, which is defined as the average of all the Hb values (from transfusion history, local, and central lab) in the

8 weeks prior to the first dose date, including the value on the first dose date (Part 1 or Part 2) and excluding values that were within 14 days after transfusion (thus considered to be influenced by transfusion) for all treated subjects. If there were no Hb values that met this definition of not being influenced by transfusions, then the baseline value (the last non-missing Hb, or the average if multiple values from the same date, from local or central lab collected on or before the first dose) is used.

For subjects who have been randomized but not treated with any study drug, the last non-missing Hb, or the average if multiple values from the same date, from local or central lab collected on or before the randomization date will be used for pretreatment Hb.

For each part of the study:

Screening Phase: up to 28 days during which subject’s eligibility will be reviewed and approved before Study Day 1.

Treatment Phase: extend from Study Day 1 until the date of the last dose. The Treatment Phase will be subdivided by cycles, based on the nominal treatment cycles as recorded on the CRF. Each cycle is planned to be 28 days.

End of Treatment Phase: between date of last dose of study drug +1 day and the End of Treatment Visit, or the earliest of (the last dose date +30 days, death date, or the last contact date if subject lost to follow-up or withdrew consent) when End of Treatment Visit is not performed. The assessments performed during the ‘End-of Treatment Visit’ will be included in this phase.

Post-treatment Follow-up Phase: Posttreatment Follow-up Phase will continue after the end of treatment phase until death, lost to follow-up, withdrawal of consent, or the End of the Study (whichever occurs first). End of Study is defined as 24 months after Randomization of the last subject in the main study of Part 2 or anytime the sponsor terminates the study, whichever comes first.

Treatment-Emergent Period: In general, the treatment-emergent period is defined as the time from first dose date through 30 days after last dose date, or the day before subsequent antineoplastic therapy, whichever occurs first.

4.2.2 Study Day

Study Day 1 is defined as the day of the first dose for subjects enrolled in Part 1 and the day of randomization for subjects enrolled in Part 2.

Study Day = assessment date – Study Day 1 + 1 for assessments performed **on or after** Study Day 1;

Study Day = assessment date – Study Day 1 for assessments performed **before** Study Day 1;

Cycle Day = assessment date – date of the first dose for the cycle + 1.

All durations are calculated as the stop date minus the start date +1 unless otherwise specified.

4.2.3 Missing or Partial Dates

In general, imputation of partial missing dates will be made for AE onset date, AE resolution date, date of death, start and end dates of concomitant therapy, and date of initial diagnosis.

For AE onset and resolution date, the global standard AE imputation rules listed below will be applied.

- Partial AE onset dates will be imputed as follows:
 - If the onset date of an adverse event is missing day only, it will be set to:
 - First day of the month that the AE occurred, if month/year of the onset of AE is different than the month/year of the first dose date;
 - The day of first dose date, if the month/year of the onset of AE is the same as month/year of the first dose date and month/year of the AE resolution date is different;
 - The day of first dose date or day of AE resolution date, whichever is earliest, if month/year of the onset of AE and month/year of the first dose date and month/year of the AE resolution date are same;
 - If the onset date of an adverse event is missing both day and month, it will be set to the earliest of:
 - January 1 of the year of onset, as long as this date is after the first dose date;
 - Month and day of the first dose date, if this date is the same year that the AE occurred;
 - Last day of the year if the year of the AE onset is prior to the year of the first dose date;
 - The AE resolution date;
 - Completely missing onset dates will not be imputed.
- Partial AE resolution dates not marked as ongoing will be imputed as follows:
 - If the resolution date of an adverse event is missing day only, it will be set to the earliest of the last day of the month of occurrence of resolution or the day of the date of death, if the death occurred in that month;
 - If the resolution date of an adverse event is missing both day and month, it will be set to the earliest of December 31 of the year or the day and month of the date of death, if the death occurred in that year;
 - Completely missing resolution dates will not be imputed;

For start and end dates of concomitant therapies, the global standard AE imputation rules listed above will be applied accordingly.

For date of death and date of initial diagnosis, the following rule will be applied.

- If date is completely missing, no imputation will be made;
- If year is missing, no imputation will be made;
- If only year is present, but, month and day are missing, then June 30th will be used;
- If only day is missing but year and month are available, then the 15th of the month will be used;

However, the above imputations will be modified by the following rules:

- If such imputed date for initial diagnosis is on or after study consent date, then consent date - 1 will be used;
- If the imputed date is for a date of death and is before the last date that the subject is known to be alive, the latter date + 1 will be used.

4.3 General Presentation Considerations

Continuous data will be summarized in terms of the mean, standard deviation (SD), median, minimum, maximum and number of observations, unless otherwise stated. Continuous data that are expected to be skewed will be presented in terms of the maximum, upper quartile, median, lower quartile, minimum and number of observations. The minimum and maximum will be reported to the same number of decimal places as the raw data recorded in the database. The mean, median, lower quartile and upper quartile will be reported to one more decimal place than the raw data recorded in the database. The SD will be reported to two more decimal places than the raw data recorded in the database. In general, the maximum number of decimal places reported shall be four for any summary statistic.

Categorical data will be summarized in terms of the number of subjects providing data at the relevant time point (n), frequency counts and percentages. Percentages will be presented to one decimal place and won't be presented for zero counts. Percentages will be calculated using n as the denominator.

Changes from baseline will be summarized using shift tables where appropriate.

P-values greater than or equal to 0.001, in general, will be presented to three decimal places. P-values less than 0.001 will be presented as "< 0.001". Confidence intervals (CI) will be presented to one more decimal place than the raw data.

In general, the analysis for Part 2 will be conducted by treatment group, for Part 1 by population type. The population type of Part 1 is specified as below:

- (1) All subjects: all subjects enrolled in Part 1;

- (2) Target population: the subjects with non-del(5q) MDS and without prior exposure to either hypomethylating agents (HMAs) or lenalidomide;
- (3) Other subjects: all Part 1 subjects excluding the subjects in the target population;

All report outputs will be produced using SAS[®] version 9.3 or a later version, and other software e.g. R as needed, in a secure and validated environment.

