Data from Part 1 of the current study demonstrated activity of imetelstat in subjects with MDS with higher rates of red blood cell (RBC) TI in subjects with non-del(5q).^{11,46} In the initial cohort of 32 MDS subjects, RBC TI was observed in 11 (34%) subjects, with a higher rate of RBC TI in 7 of the 13 (54%) subjects with non-del(5q) MDS and no prior lenalidomide or hypomethylating agent therapy. The study was amended to include only these subjects. As of the clinical cut-off date of 26 October 2018, 38 subjects (13 original and 25 additional) who had non-del(5q) MDS and no prior lenalidomide or hypomethylating agent therapy were enrolled and dosed with imetelstat. The median follow-up for the initial 13 subjects was 29.1 months and 8.7 months for the additional 25 subjects. The median number of treatment cycles was 8 (range, 1-34) and the median dose intensity was 6.9 mg/kg/cycle. The median baseline transfusion burden was 8 units/8 weeks (range, 4-14 units). The 8-week and 24-week were 14/38 (37%) subjects, and 10/38 (26%) subjects, respectively. The median time to onset of RBC TI was 8.1 weeks (range 0.1-33.1 weeks) and the median duration of RBC TI has not been achieved (17 weeks- not estimated [NE]). The mean relative reduction of RBC transfusion burden was 68%, and 8 subjects (21%) had responses by modified IWG 2006 criteria (complete remission [CR]+ marrow CR + partial remission [PR]). The 24-week RBC TI responses were accompanied by a Hb rise of ≥ 3 g/dL. The HI-E rate was 71%.

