3. STUDY DESIGN AND RATIONALE

3.1. Overview of Study Design

This is a Phase 2/3, multicenter study of imetelstat in transfusion-dependent subjects with low or intermediate-1 risk MDS that is relapsed/refractory to ESA treatment (see Inclusion Criterion 5, Section 4.1). The study will consist of 2 parts, and approximately 270 subjects may be enrolled (Figure 2). Part 1 was an open-label, single-arm design to assess the efficacy and safety of imetelstat, which enrolled 57 subjects. Part 2 is a double-blind, randomized, placebo-controlled design to compare the efficacy of imetelstat with placebo. In addition to the approximately 170 subjects to be enrolled in the main study in Part 2, approximately 45 subjects will be enrolled in a separate Ventricular Repolarization substudy. Subjects should be enrolled in the main study of Part 2 until enrollment is complete unless a subject is known to meet criteria that would make the subject ineligible for the main study (eg, del 5 q, prior HMA therapy). See Figure 2 for schematic overview of the study.

Part 1 was an open-label, single-arm design to assess the efficacy and safety of imetelstat. Fifty-seven subjects were enrolled in Part 1, including the expansion cohort, and were followed-up for safety, hematologic improvement, and reduction in transfusion requirement. The sponsor has reviewed and assessed all available data in Part 1, including blood counts, transfusion requirement, tolerability, pharmacokinetics, and pharmacodynamic biomarker data.

The futility criteria before Amendment 2 were defined as follows: If 4 or fewer subjects among 30 subjects in Part 1 achieve RBC TI lasting at least 8 weeks, the study will be stopped unless there is compelling clinical evidence of efficacy in one or more other endpoints (eg, transfusion reduction, erythroid improvement). Upon review of the efficacy and safety data observed with the 7.5 mg/kg dose among 32 subjects in Part 1, a subset of 13 subjects was identified with higher hematologic response rates. These were subjects with non-del(5q) MDS and without prior exposure to either hypomethylating agents or lenalidomide. As of Amendment 2, Part 1 was expanded to include only subjects who meet these criteria, with the goal to confirm the safety and efficacy data seen in this subset and to re-confirm the dose. Twenty-five additional subjects with non-del(5q) MDS and without prior exposure to either hypomethylating agents or lenalidomide,

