11.3. Sample Size Determination

Approximately 270 subjects (57 subjects enrolled in Part 1, approximately 170 subjects in the main study of Part 2, and approximately 45 subjects in Ventricular Repolarization substudy of Part 2) will be enrolled in the study. The initial cohort of 32 subjects enrolled into Part 1 was expanded with Amendment 2 to include an additional 25 subjects who meet the revised entrance criteria, for a total of 57 subjects in Part 1.

On the basis of historical data, the RBC TI rate is expected to be approximately 7.5%^{39,41} in subjects with low or intermediate-1 risk MDS without any active treatment. The RBC TI rate with imetelstat treatment is expected to be approximately 30% based on preliminary data from Study CP14B019. The futility criteria before Amendment 2 were defined as follows: If 4 or fewer subjects among 30 subjects in Part 1 achieve RBC TI lasting at least 8 weeks, the study will be stopped unless there is compelling clinical evidence of efficacy in one or more other endpoints (eg, transfusion reduction, erythroid improvement). The assumption was that if the RBC TI rate of 30% with imetelstat treatment is true, the probability of passing the futility criterion would be 97%.

Upon review of the efficacy and safety data observed with the 7.5 mg/kg dose among 32 subjects in the initial cohort of Part 1, a subset of 13 subjects was identified with higher hematologic response rates. These were subjects with non-del(5q) MDS and without prior exposure to either hypomethylating agents or lenalidomide. As of Amendment 2, Part 1 was expanded to include only subjects who meet these criteria, with the goal to confirm the safety and efficacy data seen in this subset and to re-confirm the dose. Twenty-five additional subjects with non-del(5q) MDS and without prior exposure to either hypomethylating agents or lenalidomide were enrolled for a total of 38 (from 57 enrolled in Part 1) that met these criteria.

Since data from Part 1 for this target population show clinical benefit of treatment with imetelstat (see Section 1.1.5 for summary of data from the 38 subjects in the target population), Part 2 of the study will be initiated.

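### The Part 1 target population pools the 13 subjects whose results defined it with the 25 enrolled to confirm it, so its TI rate is biased upward in expectation and no planned display shows the independent estimate

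*SAP*

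**What the plan says.** Protocol 3.1 and 11.3 describe how the subset arose. After efficacy and safety data from the first 32 Part 1 subjects were reviewed, "a subset of 13 subjects was identified with higher hematologic response rates". The defining features were baseline ones (karyotype and prior therapy), but they were picked out with the outcomes in view. Part 1 was then expanded by 25 subjects who met those criteria, "with the goal to confirm the safety and efficacy data seen in this subset".

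Protocol 1.1.5 gives the counts. For the first cohort: "In the initial cohort of 32 MDS subjects, RBC TI was observed in 11 (34%) subjects". The subset later chosen from that cohort contributed 7 of those responders among its 13 members (54%). At the 26 October 2018 cutoff the analysed group is "38 subjects (13 original and 25 additional"), and its 8-week TI results "were 14/38 (37%) subjects". No TI rate is given for the 25 alone.

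SAP 4.3 fixes three Part 1 populations: all subjects, other subjects, and "Target population: the subjects with non-del(5q) MDS and without prior exposure to either hypomethylating agents (HMAs) or lenalidomide". Membership of the third does not depend on cohort. SAP 4.9.2.2 adds a Part 1 forest plot over the subgroups of SAP 4.9.1.4, and that list has no initial-versus-expansion factor.

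**The concern.** When a subgroup is chosen because it responded well, part of its observed advantage is expected to be luck. Subjects enrolled afterwards under the same criteria are free of that selection, which is why an expansion cohort can confirm. Folding the selecting subjects back in returns part of the selection to the estimate.

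The side-by-side display has the same problem. The other-subjects group has 57 − 38 = 19 members, which equals 32 − 13, so all of them come from the initial cohort. Target against other therefore includes the contrast that prompted the choice of subset (7/13 against 4/19).

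What is at stake is what Part 1 can conclude. SAP section 1 says that it governs final reporting, and both documents cite benefit in the target population as the reason for opening Part 2. As specified, that report would not show whether the finding was reproduced in subjects who played no part in generating it.

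**Working it through.** **Inputs** (protocol 1.1.5 unless stated): TI in 11/32 initial subjects; 7/13 in the selected subset; 14/38 in the pooled target population; median follow-up 29.1 months for the 13 and 8.7 months for the 25; time to TI onset median 8.1 weeks, longest 33.1 weeks. Part 1 enrolled 57 (protocol 11.3).

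**Stated figures reproduced.** 11/32 = 34.4%; 7/13 = 53.8%; 14/38 = 36.8%. All agree with the protocol.

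**Expansion cohort by subtraction.** Responders: 14 − 7 = 7. Subjects: 38 − 13 = 25. Rate: 7/25 = 28.0%. This assumes that 7/13 still held at the October 2018 cutoff and uses the 8-week definition, which the sentence reporting it does not state. TI counts once achieved, so the 13 can only have gained responders, and each gain lowers the expansion figure at that cutoff: 8/13 leaves 6/25 = 24%, and 9/13 leaves 5/25 = 20%.

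**Exact (Clopper-Pearson) 95% intervals.**

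| Group | TI | Rate | 95% CI |
|---|---|---|---|
| Initial subset | 7/13 | 53.8% | 25.1–80.8% |
| Expansion (by subtraction) | 7/25 | 28.0% | 12.1–49.4% |
| Pooled target | 14/38 | 36.8% | 21.8–54.0% |
| Other initial subjects | 4/19 | 21.1% | 6.1–45.6% |

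Pooled minus expansion is 36.8 − 28.0 = 8.8 points.

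**Chance.** Fisher's exact test of 7/13 against 7/25 (odds ratio 3.0) gives p = 0.16.

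**How much selection alone could add.** Simulation with a true rate of 28% in everyone, no subset effect, and a subset of 13 kept only if it beat the other 19 by a given margin:

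- Margin above 20 points: the subset averages 45.2%, so the pooled rate averages (13 × 0.452 + 25 × 0.28)/38 = 33.9%, about 6 points too high.
- Any positive margin: the subset averages 36.1%, so the pooled rate averages (13 × 0.361 + 25 × 0.28)/38 = 30.8%, about 3 points too high.

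The observed margin was 53.8 − 21.1 = 32.8 points (from unrounded rates). True rates of 30% and 34% give similar lifts. This is an illustration; the documents do not say how many subsets were examined.

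**Follow-up, which works the other way.** 8.7 months × 365.25/12/7 = 37.8 weeks. A response starting at the latest observed onset needs 33.1 + 8 = 41.1 weeks to qualify, longer than the median follow-up of the 25. A response at the median onset needs 8.1 + 8 = 16.1 weeks, well inside it. So some later responders among the 25 were possible. Two more would give 9/25 = 36% and move the pooled rate to 16/38 = 42%.

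**The case against.** The strongest reply is that nothing inferential depends on the pooled rate. Part 1 efficacy is descriptive (SAP 4.9.2.2). Part 2 is sized on 30% from Study CP14B019, not on 37% (protocol 11.3), and is tested in newly randomized subjects; Part 1 subjects cannot enter it (protocol 3.1). The decision to open Part 2 was taken by Amendment 3 (April 2019), before SAP version 1.0 (October 2020), and 28% would hardly have changed it: it is close to 30%, and its lower limit of 12.1% lies above the 7.5% historical rate. All of this stands, and it is why the point is minor.

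Second, the provenance of the 13 is openly described, and a careful reader can do the subtraction. SAP 4.3 is prefaced as a general rule, and the subgroup list is open-ended, so a cohort split is permitted. That stands too. But permitted is not planned, and the subtraction works only for the 2018 figures and only under an assumption.

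A reader might also infer that the 37% is shown to be inflated, by about 9 points. The documents do not support that. The gap is within chance, part of it may reflect the shorter follow-up of the 25, and the 28% does not bound their final rate. Nor do they support the inference that Part 2's rationale or power is undermined.

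**Conclusion.** The point holds in limited form. As SAP 4.3 defines it, the pooled target-population TI rate is biased upward by selection in expectation, and no specified display gives the rate in the 25 independently enrolled subjects. At the 2018 cutoff the figures are 37% pooled against at most 28% in the expansion subjects, the latter resting on 7/13 being an 8-week count that had not fallen by that date. Selection alone could plausibly lift the pooled rate by about 3 to 6 points under the simulated conditions. Whether the reported rate is too high on balance is unknown, because immature follow-up in the 25 acts in the opposite direction. Part 2 is untouched. Severity: minor.

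**What to change.** In SAP 4.3, split the Part 1 target population into initial (n = 13) and expansion (n = 25). Report each at the final Part 1 cutoff with an exact 95% interval and its median follow-up. State that the expansion subjects provide the independent, confirmatory estimate, and label the pooled 38 as supportive because it contains the data that defined the subset. Footnote the target-versus-other display in the same way.

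The final data can separate selection from immaturity better than the 2018 cut, because by Amendment 8 all Part 1 subjects had stopped treatment (protocol 3.1).

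The cost is two extra table columns, wider intervals in each cohort than in the pooled group, and possibly a less favourable headline rate for Part 1. No new data are needed.
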